11.2.5 Analysis of Population Demographics, Baseline and Procedural Characteristics

Descriptive statistics will be summarized for baseline demographics, medical history, baseline disease characteristics, and procedural characteristics.

11.2.6 Analysis of Primary Safety Endpoint

For the composite primary safety endpoint, the proportion of subjects with device success and free from device- and/or procedure-related SAEs (per CEC adjudication) at 30 days. The summaries for each individual safety data point will also be provided.

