NUMBER OF Clinical Sites	Up to 6 sites within in the United States will be evaluated, qualified, and selected for participation.										
PROCEDURE AND FOLLOW-UP:	All subjects that receive an EchoMark LP will be evaluated at the following time-points: • 15 days (+/- 7 days) • 30 days (+/- 7 days) • 60 days (+/- 15 days) • 90 days (+/- 15 days) • 120 days (+/- 15 days) • 150 days (+/- 15 days) • 150 days (e month) (+/- 15 days) • 12 Month (1 Year) (+/- 15 days) • 15 Months (+/- 15 days) • 18 Months (+/- 15 days) • 24 Months (+/- 15 days) • 24 Months (+/- 15 days) Except for the 180 day (6 month), 12 month (1 year), 15 Month, 18 Month, and 24 Months visits, each visit will include a physical exam, Duplex scan, EchoSure scan, and assessment for adverse events. The monthly EchoSure scans will be suspended after the 120-day (4 month) visit or once radiographic maturation is achieved, whichever is longer, but clinical follow-up and Duplex will continue per the above schedule. The 180-day (6-month) and 12 month (1 year)visits will include a physical examination, Duplex scan for patency, and an assessment for adverse events. The 15 Month, 18 Month, and 24 Month visits will include a physical examination, Duplex scan for patency, and an assessment for adverse events. The 15 Month, 18 Month, and 24 Month visits will include capture of medical history since the last visit, a duplex scan, information on any fluid collection observed on the Duplex scan, and an assessment for any adverse events. EchoSure scans will be completed by study personnel who do not have prior ultrasound training and are representative of non-expert users. Subjects that are consented but do not receive the EchoMark LP will be considered a screen failure, and can be replaced.										
Primary Endpoint	The primary safety and feasibility endpoints are as follows:										
	Primary Safety:										

	 Composite of new major device related adverse events (MAEs) at 30 days post EchoMark LP implantation, as adjudicated by the Clinical Events Committee (CEC), including: Device or procedure-related death Device related infection Device related interventions Device related hospitalizations Fistula failure Fistula rupture Aneurysm 							
	After the close of the final 90-day visit window, all evaluable subjects will be summarized and expansion to a pivotal trial will be requested under a new IDE.							
	Primary Feasibility (Technical Success):							

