4.2 Study Endpoints

4.2.1 Primary Safety Endpoints

Composite of new major device related adverse events (MAEs) at 30 days post EchoMark implantation, as adjudicated by the Clinical Events Committee (CEC) including:

- Device or procedure-related death
- Device related infection
- Device related interventions
- Device related hospitalizations
- Fistula failure
- Fistula rupture
- Aneurysm

After the close of the 90-day visit window, all evaluable subjects will be summarized and expansion to a pivotal trial will be requested under a new IDE.

4.2.2 Primary Feasibility (Technical Success):

Rate of Technical Success defined as the successful implantation of the EchoMark implant and the ability to determine blood flow, diameter and depth measurements using the EchoSure diagnostic ultrasound system from baseline to 4 months.

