9.1 Serious Adverse Event

An adverse event (AE) or suspected adverse reaction is considered "serious" if, in the view of either the investigator or sponsor, it results in any of the following outcomes: death, a life-threatening adverse event, in subject hospitalization or prolongation of existing hospitalization, a persistent or significant incapacity or substantial disruption of the ability to conduct normal life functions, or a congenital anomaly/birth defect. Important medical events that may not result in death, be life-threatening, or require hospitalization may be considered serious when, based upon appropriate medical judgment, they may jeopardize the participant and may require medical or surgical intervention to prevent one of the outcomes listed in this definition.

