11.2. Data Analysis Plan

11.2.1 General Principles

All statistical analyses will be performed using Statistical Analysis System (SAS) for Windows (version 9.4, SAS Institute Inc. Cary, NC), STATA (version 16, StataCorp, College Station, TX) or other widely accepted statistical or graphical software. All statistical analysis will be conducted by an independent statistician.

Descriptive statistics will be used to present the data and to summarize results. Discrete variables will be presented using frequency distributions and cross tabulations. Continuous variables will be summarized by presenting the number of observations (N), mean, standard deviation, median, minimum, and maximum values. In general, data for all study subjects combined will be presented. The primary analysis for all baseline characteristics and study outcomes will include all available data for all enrolled subjects. Individual data will be presented in subject listings.

Summaries of the following endpoints present the number and percentage of unique subjects within an event, unless specified otherwise: protocol deviations; subject status; adverse events. Thus, multiple occurrences of the same event are counted only once per subject, unless specified otherwise.

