11.2.4 Analysis Samples

The primary and observational analysis samples will include all enrolled subjects with successful EchoMark LP implantation.

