11.2.7 Analysis of Primary Feasibility (Technical Success)

Definition of feasibility endpoints are described in Section 4.2.

For composite endpoints, i.e., technical success and implantation success, the number and percentage of subjects with success will be summarized. Descriptive statistics for components of each endpoint will also be provided.

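### The primary safety analysis in Section 11.2.6 estimates a different quantity from the 30-day MAE composite declared in Sections 2 and 4.2.1, and relies on an undefined term

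*Combined protocol and SAP*

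**What the plan says.** **Declared endpoint.** Section 4.2.1 gives primary safety as "Composite of new major device related adverse events (MAEs) at 30 days post EchoMark implantation, as adjudicated by the Clinical Events Committee (CEC) including" seven items: death related to device or procedure; device-related infection, interventions and hospitalizations; fistula failure; fistula rupture; and aneurysm. The protocol summary in Section 2 declares the same composite, "new major device related adverse events (MAEs) at 30 days post EchoMark LP implantation", with the same list. Neither place requires an event to be serious.

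**Planned analysis.** Section 11.2.6 says that for the composite primary safety endpoint the quantity is "the proportion of subjects with device success and free from device- and/or procedure-related SAEs (per CEC adjudication) at 30 days". It adds: "The summaries for each individual safety data point will also be provided".

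**Related text.**
- Section 9.1 defines a serious adverse event (SAE) by outcome, including "in subject hospitalization or prolongation of existing hospitalization", or by medical judgment for other important events.
- Section 11.2.7 speaks of other kinds of success: "For composite endpoints, i.e., technical success and implantation success".
- Section 11.2.4 limits the analysis samples to "all enrolled subjects with successful EchoMark LP implantation".
- Section 11.2.1 states the counting rule for adverse events: "multiple occurrences of the same event are counted only once per subject, unless specified otherwise".

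**The concern.** The section that should turn the declared endpoint into a number defines a different number. The MAE list goes by type of event and mainly by relation to the device. The 11.2.6 proportion goes by seriousness, admits procedure-related events of every kind, and adds a success condition that the text never defines. Sections 11.2.7 and 11.2.8 refer back to Section 4.2 for their definitions; Section 11.2.6 does not.

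A descriptive feasibility study delivers estimates and nothing else. If its main safety estimate does not match its declared safety endpoint, a reader cannot tell which rate is being reported, and whoever runs the analysis must choose a meaning for 'device success', possibly after seeing the data. Sections 2 and 4.2.1 also say that evaluable subjects will be summarized after the 90-day window and expansion to a pivotal trial then requested, so the ambiguous figure may be carried into that request.

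**Working it through.** The plan states no target, threshold or expected rate for primary safety, so there is no design figure to reproduce. The check compares the definitions and then sizes the gap with assumed counts.

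**Step 1: classify a subject under each definition.** Inputs are the list in Section 4.2.1, the SAE definition in Section 9.1 and the wording of Section 11.2.6. Except in the last row, 'device success' is taken as met.

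| Subject's only occurrence by day 30 | 4.2.1 composite | 11.2.6 proportion |
|---|---|---|
| Device- or procedure-related death | event | failure |
| Device-related hospitalization | event | failure |
| Device-related infection or intervention not judged serious | event | counted as event-free |
| Hospitalization related to the fistula procedure but not the device | no event | failure |
| No adverse event, 'device success' not met | no event | failure |

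The third row makes 11.2.6 look better than the declared endpoint; the last two make it look worse. The net direction is therefore not determined.

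**Step 2: test the possible meanings of 'device success'.**
- If it means implantation success, everyone in the Section 11.2.4 sample has it by construction and it adds nothing.
- If it means technical success, Section 4.2.2 assesses that from baseline to 4 months. It is incomplete at day 30, and for late enrollees also at the interim analysis, which Section 11.2.9 places at the last subject's 90-day visit.

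**Step 3: can the component summaries replace the composite?** Under Section 11.2.1 a subject is counted once within each event, so one subject can appear under several components. One infection, one intervention and one hospitalization could come from a single subject or from three.

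**Step 4: size at n = 20** (the maximum main enrolment in Section 11.1). One subject is 1/20 = 5 percentage points. Exact 95% limits for x of n are the 2.5% quantile of Beta(x, n − x + 1) and the 97.5% quantile of Beta(x + 1, n − x). With x = 0 the upper limit is 1 − 0.025^(1/20) = 16.8%. All event counts below are assumed.

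- *Case A:* two subjects each have a non-serious device-related MAE, and all meet 'device success'. Section 4.2.1 gives 2/20 = 10.0% with an event (1.2% to 31.7%). Section 11.2.6 gives 0/20 with an event (upper limit 16.8%), that is 20/20 successes (lower limit 83.2%).
- *Case B:* no MAE, one procedure-related non-device hospitalization, and one other subject who fails 'device success'. Section 4.2.1 gives 0/20 with an event (upper limit 16.8%). Section 11.2.6 gives 18/20 = 90.0% success (68.3% to 98.8%). If 'device success' means implantation success, the second failure cannot occur and the figure is 19/20 = 95.0% (75.1% to 99.9%).
- *Components in Step 3:* 1/20 = 5.0% (0.1% to 24.9%) if one subject had all three events, or 3/20 = 15.0% (3.2% to 37.9%) if three subjects had one each.

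**The case against.** The strongest reply is that this is a drafting slip with little consequence. Section 11.1 sets no hypothesis, the results are descriptive, the components will be tabulated, and the composite can be rebuilt from the subject listings. Section 11.2.6 opens by naming the composite endpoint, and its sentence lacks a main verb, so it may be a fragment and not a deliberate replacement. Section 11.2.1 provides frequency distributions for discrete variables generally, and Section 12.7 has the CEC provide a final analysis of all safety endpoints. Either could be read as covering the declared composite.

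It is true that no decision rule or error rate is affected and that the data will exist. But general defaults do not override a rule written for this endpoint, and rebuilding a rate from listings is not a specified analysis.

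Three narrower points have some force:
- 'Major' is undefined. If it meant serious, the non-serious MAE gap would largely close. No text says so, and the procedure-related hospitalization and the undefined success term would remain. Section 9.1 also lets many interventions be judged serious, so the gap concerns only MAEs that are not.
- The denominator may not be 20. Section 5.1 allows up to 3 roll-in subjects per site at up to 6 sites, and Section 11.2.4 does not exclude them. The maximum would then be 20 + 18 = 38, or 1/38 = 2.6 points per subject. With the 4 sites named in Section 11.1 it would be 20 + 12 = 32, or 1/32 = 3.1 points.
- At 12 months the plan prints both the MAE composite and the SAE-free proportion. There the composite is not replaced; the two are only run together.

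**Conclusion.** The concern holds. Followed as written, Section 11.2.6 reports a headline primary safety figure that is not the declared endpoint, and one of its conditions cannot be applied without guessing. Each discordant subject is worth 5 points at n = 20, or about 2.6 to 3.1 points if the maximum number of roll-ins is included. The direction may be either way. The mismatch itself follows from the documents' own definitions. The size rests on assumed event counts, and Case B also depends on how 'device success' is read. The effect is confined to the reported primary safety rate and whatever relies on it.

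**What to change.** - Rewrite Section 11.2.6 as the number and percentage of subjects with at least one CEC-adjudicated MAE from the Section 4.2.1 list through day 30, with each component shown beneath. An exact 95% interval would be useful but is optional in a descriptive plan.
- Take 'device success' out of the safety proportion, or define it and report it on its own line.
- Keep freedom from device- and/or procedure-related SAEs as a separately labelled summary.
- Make the same separation for the 12-month measure in Sections 2, 4.2.3 and 11.2.8.11.

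The cost is minor wording changes in the protocol and analysis sections. No new data are needed, because under Section 12.7 the CEC already adjudicates all safety endpoints and reported events. The reported safety figure may rise or fall as a result.

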11.2.7 Analysis of Primary Feasibility (Technical Success)

Definition of feasibility endpoints are described in Section 4.2.

For composite endpoints, i.e., technical success and implantation success, the number and percentage of subjects with success will be summarized. Descriptive statistics for components of each endpoint will also be provided.

11.2.8 Analysis of Observational Endpoints

Observational endpoints are defined in Section 4.2.

For discrete endpoints, the number and percentage of subjects with success will be summarized. Descriptive statistics for components of each endpoint will also be provided.

For continuous variables (e.g., volume flow, depth, and diameter), results will be summarized with the with the numbers of observations, means, medians, standard deviations, minimums, and maximums. Change from baseline will be included using these same descriptive statistics.

11.2.8.1 Comparison of EchoSure volume flow, diameter and depth to Duplex values:

The degree of correlation between paired EchoSure values and Duplex values that pass the quality checks by an Independent RVT will be analyzed.

The comparison data points are:

- EchoSure vessel depth at EchoMark vs Duplex vessel depth at EchoMark
- EchoSure vessel diameter at EchoMark vs Duplex vessel diameter at EchoMark
- EchoSure volume flow at EchoMark vs Duplex volume flow at cannulation zone (standard of care)

All Duplex volume flow, depth and diameter data points will undergo quality checks performed by an Independent RVT to qualify for inclusion in the comparison analyses. The quality checks will assess if the Duplex data was collected per protocol and meet defined requirements that ensure a uniform technique.

Duplex volume flow data points that do not pass the quality checks will not be included in the analysis. The paired EchoSure flow values for failing Duplex values will also not be included.

Duplex diameter and depth values that do not pass the quality checks will be corrected by an Independent RVT. The corrected Duplex depth and diameter data points will be included in the analysis along with their paired EchoSure values.

All sites and their sonographers will be trained on the Duplex data collection protocol and quality requirements. Each site will be required to submit a set of images for quality checks by an Independent RVT as a part of site qualification.

Degree of correlation between paired EchoSure values and Duplex values (volumetric flow, vessel diameter, vessel depth, etc.) that pass quality checks will undergo the following analyses:

- Pearson Correlations to assess correlation
- Bland Altman testing using percentages will be used to assess for bias and the limits of agreement
- Distribution of correlation percentage between EchoSure and Duplex values

Additional statistical analyses may be conducted as deemed necessary.

11.2.8.2 Comparison of EchoSure depth measurements to Independent Reviewer measured depth results.

All EchoSure images will be adjudicated for the reported depth measurements. An Independent Reviewer will manually measure the vessel depth on the EchoSure images. The Independent Reviewer will only receive anonymized EchoSure images.

Degree of correlation between paired EchoSure values and the Independent Reviewer values (depth) will undergo the following analyses:

- Pearson Correlations to assess correlation.
- Bland Altman testing using percentages will be used to assess for bias and the limits of agreement.

• Distribution of correlation percentage between EchoSure and Independent Reviewer values.

Additional statistical analyses may be conducted as deemed necessary.

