7.6 Pre-Maturation Follow-up at 15, 30, 60, 90, 120, 150 Days

Subjects will have follow-up visits at 15 (+/- 7 days), 30 (+/- 7 days), 60 (+/- 15 days), 90 (+/- 15 days), 120 (+/- 15 days), and 150 (+/- 15 days) days from the baseline procedure, including a physical exam, duplex imaging, EchoSure scan, external EchoMark measurement, medical history, and adverse event monitoring. The EchoSure scans will be suspended after the 120 day (4 month) visit or once radiographic maturation is achieved,

whichever is longer. Radiographic maturation is defined as 500mL/min and a 5 mm diameter. The monthly clinical follow-up and duplex imaging will continue per the follow-up schedule. The physical exam will include assessing the fistula for bruit and thrill. The medical history will include all interventions, cannulation history including any attempts, and the most recent Kt/V, CBC, Serum Chemistry, Calcium, Phosphorous, Magnesium, Total Protein, Albumin, PTH. EchoSure scans will be completed by study personnel who do not have prior ultrasound training, are representative of non-expert users, and have been delegated on the delegation of authority log. Duplex and EchoSure scans will include:

- A total of three (3) EchoSure scans performed at the site of the EchoMark. Volume flow, diameter, and depth data to be recorded.
- A total of three (3) limited DUS scans performed at the site of the EchoMark. DUS will be performed in transverse Bmode and longitudinal view. Volume flow, diameter, depth, and distance from scan area to anastomosis will be recorded.
- A total of three (3) limited DUS scans performed at the cannulation zone in transverse Bmode and longitudinal view. Volume flow, diameter, and depth, will be recorded.
- The 9 Duplex images will be de-identified and undergo quality control checks performed by an Independent RVT.
- A duplex exam of the fistula from the EchoMark location and beyond to assess for the presence of stenotic lesions. If a lesion is present, capture and save an image showing a longitudinal view of the fistula segment with the stenosis, note the location of the stenosis in relation to the anastomosis and EchoMark, and track the stenosis as an adverse event.
- A duplex scan of the brachial artery to assess flow and diameter, capture a PW image showing the flow and diameter measurements.

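### Flow agreement is planned only across two vessel sites; the same-site Duplex flow already being recorded should be named as a second comparison

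*Combined protocol and SAP*

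**What the plan says.** Section 11.2.8.1 lists three comparisons between EchoSure and Duplex. Depth and diameter are matched on location; the diameter entry, for example, reads "EchoSure vessel diameter at EchoMark vs Duplex vessel diameter at EchoMark". The flow entry is not matched: "EchoSure volume flow at EchoMark vs Duplex volume flow at cannulation zone (standard of care". The agreement method is the same for all three: "Bland Altman testing using percentages will be used to assess for bias and the limits of agreement", together with Pearson correlation.

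The same-site Duplex flow exists. At the pre-maturation visits Section 7.6 requires three EchoSure scans at the marker and also "A total of three (3) limited DUS scans performed at the site of the EchoMark", for which "Volume flow, diameter, depth, and distance from scan area to anastomosis will be recorded". Three further Duplex scans, again with flow, are taken at the cannulation zone. Section 11.2.8.1 adds that "All Duplex volume flow, depth and diameter data points will undergo quality checks performed by an Independent RVT", so the same-site flow values are to be checked as well as collected.

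Elsewhere, Section 11.2.8 states "For continuous variables (e.g., volume flow, depth, and diameter), results will be summarized" with the usual descriptive statistics, and Section 11.2.1 states "Individual data will be presented in subject listings". Section 11.2.8.1 ends by allowing further analyses at discretion, without naming any.

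**The concern.** Section 4.2.3 promises a comparison of EchoSure and Duplex flow, and flow rate is the first measurement named in the indication (Section 3.4). A reader will take the flow bias and limits as a statement about how well EchoSure agrees with Duplex. Because the two readings come from different points on the vessel, a bias could be a device effect, a site effect or both. Components of opposite sign could cancel and leave a bias near zero. Section 4.2.1 says expansion to a pivotal trial will be requested, so a flow bias of unknown origin would be a weak planning input.

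**Working it through.** The documents state no precision or agreement figure for flow, so there is none to reproduce. The check is an identity followed by illustrations. **Every numerical input below is an assumption**; the documents give no error CV, no site difference and no direction for one.

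**Step 1: identity.** Write E for EchoSure at the EchoMark, Dm for Duplex at the EchoMark and Dc for Duplex at the cannulation zone.

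ln(E/Dc) = ln(E/Dm) + ln(Dm/Dc)

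The planned pair (left side) is the same-site method difference plus the site difference as Duplex sees it. Observing only the left side cannot split it.

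**Step 2: different causes, same planned result.** Assume a Duplex log-error SD of 0.10 and, for the simulation, a log-SD between fistulae of 0.40. The cross-site log variance is (method SD)² + (site SD)² + 0.10²; the same-site variance is (method SD)² + 0.10². Percentage Bland-Altman results from 200,000 simulated pairs:

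| Case | Method log bias, SD | Site log difference, SD | Cross-site (planned): bias, limits | Same-site: bias, limits |
|---|---|---|---|---|
| A | 0.15, 0.20 | 0, 0 | +14.8%, -28 to +58 | +14.8%, -28 to +58 |
| B | 0, 0 | 0.15, 0.20 | +14.8%, -28 to +58 | 0.0%, -20 to +20 |
| C | 0.075, 0.1414 | 0.075, 0.1414 | +14.8%, -28 to +58 | +7.5%, -26 to +41 |
| D | 0.15, 0.10 | -0.15, 0.17 | 0.0%, -43 to +43 | +14.9%, -13 to +42 |

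In A, B and C the cross-site variance is 0.05 each time (0.04+0+0.01; 0+0.04+0.01; 0.02+0.02+0.01). The planned output is therefore the same although the causes differ. Pearson r is 0.85 to 0.86 in all three. Case D is cancellation.

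**Step 3: size for a flow loss between sites.** Let F be true flow at the EchoMark and L the fractional loss to the cannulation zone (Beta-distributed, mean m). E = F × error, Dc = F(1-L) × error, with independent mean-one lognormal errors of 15% CV. Percent difference = 100(E-Dc)/[(E+Dc)/2]; limits = bias ± 1.96 SD; 2,000,000 draws. Widths come from unrounded limits.

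| Mean loss m | SD of loss | Bias | Limits | Width |
|---|---|---|---|---|
| 0 (same as same-site) | 0 | 0.0 | -40.9 to +40.9 | 81.8 |
| 5% | m/2 | +5.1 | -36.1 to +46.3 | 82.5 |
| 10% | m/2 | +10.5 | -31.7 to +52.8 | 84.4 |
| 15% | m/2 | +16.4 | -27.8 to +60.6 | 88.5 |
| 5% | m | +5.2 | -37.0 to +47.4 | 84.4 |
| 10% | m | +11.0 | -36.1 to +58.1 | 94.2 |
| 15% | m | +17.7 | -38.8 to +74.2 | 113.0 |

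Hand check of bias for a fixed loss: 200L/(2-L) gives 5.1, 10.5 and 16.2 at 5, 10 and 15%.

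Variations:
- *Error CV 10%* (same-site width 55.1): widths 55.9/59.1/65.2 with SD m/2, and 59.0/72.7/96.3 with SD m.
- *Error CV 20%* (same-site width 107.8): widths 108.1/109.6/112.4 and 109.7/117.1/132.1.
- *Site difference in both directions around zero*, SD 5/10/15%, error CV 15%: bias stays near zero (0.1/0.5/1.1) and width is 84.0/90.3/99.7.
- *Cancellation*: a device reading 10% low, with no random error and a 10% mean loss, shows +0.2 to +0.7 cross-site. Same-site it shows 200(0.90-1)/(1.90) = -10.5.

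**Step 4: can the other output supply the missing limits?** Hold the total log-SD at 0.5 with median flow 800 mL/min. Both methods then show mean 906 and SD 483 mL/min whatever the error CV, while the paired limits are ±14, ±28, ±41 or ±66% for error CVs of 5, 10, 15 or 25%. Unpaired summaries cannot give the limits. Listings would allow pairing by hand, but no same-site bias or limits are planned from them.

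**The case against.** - **The comparison is deliberate.** It is labelled standard of care, and if the question is agreement with flow as measured in practice, the site difference is part of the answer. This stands as a reason to keep the pair. It does not make it a same-location method comparison, which the plan does provide for depth and diameter. The Investigator's Brochure and some bench text are not visible, so no claim is made that the choice lacks a rationale.
- **Summary means could show the bias.** A mean of paired differences equals a difference of means. In the cancellation case with the Step 4 flow distribution, the means would be 816 (EchoSure), 907 (Duplex at the EchoMark) and 816 mL/min (Duplex at the cannulation zone), so the under-reading would be visible. That is correct if flow is tabulated by method and site on the same visits. The plan commits to no such table, and it would still give no limits.
- **The list may simply be incomplete**, since all Duplex flow values are checked so that they can enter the comparisons, and further analyses are allowed. Permission is not a commitment. Section 11.2.9 lets the sponsor access data at any time, so a pair chosen later could be chosen after seeing results.
- **Small width changes cannot be detected.** With up to 20 subjects and a difference SD of about 20.9% (40.9/1.96), 20 independent pairs give about ±10 points on the bias (2.09 × 20.9/√20) and a standard error of about 8 points on each limit. A change from 82 to 84 or 88 is within noise. This stands; the argument rests on what can be identified, not on detecting small changes.
- **Same-site Duplex flow may be noisier.** At an assumed 25% Duplex CV with EchoSure at 15%, same-site limits are -53.4 to +57.2 (width 110.6, bias +1.9). This also stands, and tighter limits are not promised.

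**Conclusion.** The concern holds. Followed as written, the plan yields a flow bias and limits that pool method disagreement with any site difference, although the data to separate them are collected and checked. That conclusion follows from the identity and needs no assumed figure.

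The size does depend on assumptions. For mean losses of 5 to 15%, the added bias is roughly the size of the loss. Added width ranges from negligible to about 31 points (113.0 - 81.8) at 15% error CV. If flow is the same at both sites, the effect is zero, and the documents do not say whether it is.

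The weight is modest. The study is descriptive with exploratory inference, no agreement margin is set, and neither primary endpoint is touched. The change is worth making because it bears directly on the flow comparison the study promises.

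**What to change.** In the Section 11.2.8.1 list:

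1. Add a same-site flow entry pairing EchoSure flow with Duplex flow, both measured at the EchoMark at the same visit, using Duplex scans that pass the quality checks. Analyse it with the methods already listed.
2. Keep the existing flow entry and call it the standard-of-care comparison.
3. Report the paired Duplex difference, EchoMark minus cannulation zone (mean and SD), so that the site component is visible.

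Use the same rule for pairing the three scans per visit and for handling repeat visits in both flow comparisons.

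The cost is one comparison and one summary, with no new data collection. Failing Duplex flow values are excluded, not corrected, so the number of usable same-site pairs is unknown and should be reported. The same-site result is agreement with Duplex, not pure device error, and its limits may be wider. That is why both pairs should be shown.
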